**CONFIDENTIAL**

N	Current PEP Rate	Assuming current PEP rate	Assuming 9.7% PEP rate	
11	4.62%	100%	100%	0.0164*
12	5.04%	100%	100%	0.0267
15	6.30%	100%	99%	0.0880
20	8.40%	99%	97%	0.3157
25	10.50%	79%	90%	0.3804
29	12.18%	28%	79%	0.1890
30	12.61%	19%**	76%	0.1539
35	14.71%	1%**	54%	0.0463
40	16.81%	0%**	32%	0.0107
43	18.07%	0%**	21%	0.0040
44	18.49%	0%**	18%**	0.0028

\*Stop for superiority

N	Current PEP Rate	Assuming current PEP rate	Assuming 9.7% PEP rates	
17	7.14%	100%	100%	0.0165*
18	7.56%	100%	100%	0.0250
20	8.40%	100%	100%	0.0515
25	10.50%	100%	98%	0.1967
30	12.61%	91%	93%	0.4455
35	14.71%	42%	82%	0.2979
37	15.55%	22%	76%	0.2160
38	15.97%	15%**	72%	0.1811
40	16.81%	5%**	64%	0.1234
45	18.91%	0%**	41%	0.0399
50	21.01%	0%**	21%	0.0102
51	21.43%	0%**	18%**	0.0076

\*\*Stop for futility

**Second Interim Analysis (n=545 per arm)**

Control arm PEP rate ≈ 9.7% (n=53)				
Subjects with PEP in Experimental Arm		Conditional Power		One-Sided Chi-Sq p-value
N	Current PEP Rate	Assuming current PEP rate	Assuming 9.7% PEP rate	
35	6.42%	100%	100%	0.0227*
36	6.61%	100%	100%	0.0300
40	7.34%	100%	100%	0.0793
50	9.17%	100%	100%	0.3780
54	9.91%	100%	100%	0.4595
55	10.09%	99%	99%	0.4197
60	11.01%	90%	98%	0.2434
70	12.84%	21%	83%	0.0518
71	13.03%	15%**	81%	0.0430
80	14.68%	0%**	46%	0.0062
87	15.96%	0%**	20%	0.0010
88	16.15%	0%**	17%**	0.0008

\*Stop for superiority

Control arm PEP rate ≈ 13% (n=71)				
Subjects with PEP in Experimental Arm		Conditional Power		One-Sided Chi-Sq p-value
N	Current PEP Rate	Assuming current PEP rate	Assuming 9.7% PEP rate	
50	9.17%	100%	100%	0.0214*
51	9.36%	100%	100%	0.0273
60	11.01%	100%	100%	0.1528
68	12.48%	100%	100%	0.3927
69	12.66%	99%	100%	0.4282
70	12.84%	99%	100%	0.464
71	13.03%	99%	100%	0.5
72	13.21%	98%	99%	0.4643
80	14.68%	66%	95%	0.215
87	15.96%	20%	82%	0.0843
88	16.15%	15%**	78%	0.0723
90	16.51%	9%**	72%	0.0524
100	18.35%	0%**	31%	0.0079
103	18.90%	0%**	21%	0.0041
104	19.08%	0%**	18%**	0.0032

\*\*Stop for futility

The SDMC will be responsible for conducting these analyses and compiling the reports for the DSMB. Since several factors need to be taken into consideration before stopping a study, safety and study progress also will be taken into consideration by the DSMB and NIDDK in the decision to stop the study if the futility boundary is crossed.

**9.3 Secondary Outcome Variable Analysis**

Analysis of the secondary outcome, the proportion of subjects with moderate-severe PEP, will be analyzed in a similar manner as the primary outcome.

We also will examine the impact of pre-specified characteristics on the primary and secondary outcomes. Specifically, the goal of this analysis is to examine prognostic variables and their impact on the primary analysis. We also will explore subgroup populations for future hypothesis generation. The baseline variables that will be examined are: age (continuous), gender, race, body mass index (continuous), suspicion of sphincter of Oddi dysfunction, prior post-ERCP pancreatitis, history of recurrent pancreatitis, manometrically documented sphincter of Oddi dysfunction, difficult cannulation, pre-cut (access) sphincterotomy, pancreatic sphincterotomy, pancreatic acinarization, biliary sphincterotomy, pancreatic stent placement, double wire technique, make/model/length/caliber of pancreatic stent, trainee involvement, prophylactic stent characteristics, type of sphincter of Oddi dysfunction, and inpatient vs. outpatient status. The assessment of each of these variables will be conducted using a logistic regression model with the dichotomous primary outcome, PEP event. Treatment arm will be a main effect in the model and the above covariates examined. Each covariate will be assessed individually first with a model that includes interaction effect with the treatment. If a significant interaction is observed ( $p < 0.10$ ), then exploratory subgroup analyses will be considered. For each model, we will be looking at the parameter estimate of the covariate to examine its association with outcome. We also will be examining the parameter estimate of the treatment in the presence of the covariate. A multivariable model will be created based on the results of the individual models (a combination of statistical and clinical significance will be used for model inclusion). The final multivariable model will be based on goodness of fit criteria. For this final model, the adjusted risk difference will be estimated with a 95% confidence interval. If the upper limit of this confidence interval is 5% or greater, then non-inferiority of the treatments cannot be concluded in the presence of the particular covariates. This analysis will be run on both the ITT and PP analysis populations.

For the multivariable model, it is possible that several of the baseline characteristics will be eligible for the model. In this case, we will derive a risk score based on the methods used in the previous indomethacin trial. Individual patient risk scores will be determined by assigning one point for each major inclusion criteria and 0.5 points for each minor inclusion criteria (see below table). Similar to the above methods, the derived risk score will be examined for inclusion in the final multivariable model. In addition to the risk score, we will use a propensity score approach to derive a baseline variable that describes the baseline risk. The results of each risk score approach will be compared to provide helpful information for future trials.

Major Risk Criteria (1pt each)	Minor Risk Criteria (0.5pts each)
Suspicion of SOD	Age < 50
Prior post-ERCP pancreatitis	Female gender
Difficult cannulation	History of recurrent pancreatitis
Pre-cut sphincterotomy	
Pancreatic sphincterotomy	

Several procedures have been incorporated into the study design (i.e., procedure manual, training, protocol violation monitoring, outcome adjudication) to reduce center effects; however, these effects should not be ignored for this trial. As a secondary analysis of the study outcomes, a two-sided confidence interval for the difference in the PEP event rate between the two treatment arms will be calculated using the Newcombe method, stratifying by site. Non-inferiority will be concluded if the upper limit of the confidence interval is less than 5%. Similar to the assessment of potential prognostic variables, the results of this secondary analysis will be taken into account when interpreting the final results of the trial.

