13.3 Statistical Analyses

An intention-to-treat approach will be the primary basis for analysis. For the analysis of the primary and secondary endpoints, the two-sided 95% upper confidence bound (equivalent to the one-sided 97.5% upper confidence bound) of the observed risk difference in the proportion of patients developing post-ERCP pancreatitis (or moderate-severe PEP) between the two treatment groups (indomethacin alone – combination of indomethacin and PSP) will be calculated. Indomethacin alone will be declared non-inferior to combination therapy if the two-sided 95% upper confidence bound of the treatment difference is less than 5%. If indomethacin is found to be non-inferior, an analysis for superiority will be conducted using a one-sided two sample test for independent binomial proportions.²⁴

Exploratory subgroup analyses will be performed as specified in the Statistical Analysis Plan (SAP). These exploratory subgroup analyses will allow the development of hypotheses about subgroups of patients that may particularly benefit from PSP.

All statistical analyses are outlined in the study Statistical Analysis Plan.

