## 9. EFFICACY ANALYSIS

### 9.1 Primary Outcome Variable Analysis

The analysis of the primary outcome is the difference ( $p_i - p_c$ ) between the two treatment arms in the observed proportion of patients experiencing PEP. This difference will not be adjusted for covariates. However as a secondary analysis of the primary outcome, prognostic variables will be examined as described in detail below. Non-inferiority will be assessed on both the intention-to-treat and per protocol populations (defined above) at the one-sided 2.5% significance level by using the upper bound of the two-sided 95% confidence interval for the difference in PEP event rates. Non-inferiority can be claimed if both analysis populations show non-inferiority (i.e., the two-sided confidence interval is less than 5%).

If (and only if) non-inferiority is claimed, an analysis for superiority will be conducted using a one-sided two-sample test for independent binomial proportions. This test will be conducted at a 0.025 significance level.

Due to a protocol amendment that resulted in a change in the timing of the indomethacin administration (from end of procedure to time of randomization), we have included a sensitivity analysis of the primary outcome. The above analysis will be repeated only including those randomized under the new protocol where indomethacin should be administered at time of randomization. We also will examine the PEP rates in the population that was treated with indomethacin post-

ERCP (initial protocol) as compared to those treated at time of randomization.

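### Moderate-severe PEP gets its own formal non-inferiority and superiority claims, with no testing order or alpha link to the primary endpoint

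*SAP*

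**What the plan says.** Protocol 2.2 lists non-inferiority on the severity of PEP as a secondary objective, so the endpoint is inferential by design. Protocol 13.3 then sets one decision rule for both endpoints. It opens with "For the analysis of the primary and secondary endpoints, the two-sided 95% upper confidence bound" and continues: "Indomethacin alone will be declared non-inferior to combination therapy if the two-sided 95% upper confidence bound of the treatment difference is less than 5" percent. A superiority analysis follows if non-inferiority is found.

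SAP 9.1 sets the levels for the primary. Non-inferiority is judged at one-sided 2.5% and must hold in both the intention-to-treat and per-protocol samples. Then: "If (and only if) non-inferiority is claimed, an analysis for superiority will be conducted using a one-sided two-sample test for independent binomial proportions". Of that test it says: "This test will be conducted at a 0.025 significance level".

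SAP 9.3 carries this over to the secondary endpoint: "Analysis of the secondary outcome, the proportion of subjects with moderate-severe PEP, will be analyzed in a similar manner as the primary outcome".

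Neither document states an order between the two endpoints, makes the secondary claim conditional on the primary, splits alpha, or calls the secondary analysis descriptive. The only joint condition is the one on analysis samples. The only adjusted level is the two-tailed 0.01 for subgroup analyses in SAP 9.4, which does not cover the secondary endpoint.

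**The concern.** Within an endpoint the order is clear: superiority only after non-inferiority. Between the endpoints there is none. Two things follow.

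First, if PEP fails non-inferiority, the text still permits a formal, pre-specified declaration of non-inferiority on moderate-severe PEP. It would be reported beside a failed primary, for an endpoint that is a subset of the primary, and the reader would have no rule for weighing the two.

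Second, there are two routes to a superiority claim, each at one-sided 2.5%. The chance that at least one is false is therefore above the 2.5% stated for each test.

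The primary conclusion itself is unaffected. What is at stake is which further claims the trial may formally make.

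**Working it through.** **Inputs.** Margin 5% absolute and one-sided 2.5% tests (Protocol 13.3, SAP 9.1); control PEP rate 9.7%, with 13% as the high scenario (SAP 4.2, 4.3); 1090 per arm (Protocol 1.0). The moderate-severe share of PEP is not given. Protocol 3.1 gives only a 12% severe share, so the moderate-severe share is an assumption, varied from 10% to 80%.

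**The plan's own figure.** Power at 650 per arm with equal rates is Φ(0.05/√(2p(1−p)/650) − 1.96).
- p = 0.097: 0.05/0.01642 = 3.046; Φ(1.086) = 86.1% (stated 85%).
- p = 0.13: 0.05/0.01866 = 2.680; Φ(0.720) = 76.4% (stated 76%).

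The closed formula gives 630 per arm for 85% power; adding a continuity term of 1/0.05 = 20 brings it to about 649, against the stated 650. The design inputs are therefore understood correctly. The plan states no figure for multiplicity.

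**False superiority with equal arms.** Let p be the PEP rate and p_s = p × share the moderate-severe rate. Because the second endpoint is nested in the first, the covariance of the two indicators is p_s(1−p), so

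ρ = √[p_s(1−p) / (p(1−p_s))].

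The chance of at least one false claim is 0.025 + 0.025 − P(both), with P(both) from the bivariate normal with correlation ρ. Example at p = 0.097 and a 30% share: p_s = 0.0291; ρ = √(0.0291×0.903 / (0.097×0.9709)) = 0.528; P(both) = 0.0050; result 0.050 − 0.0050 = 4.5%.

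| Share of PEP that is moderate-severe | At least one false superiority claim | Ratio to 2.5% |
|---|---|---|
| 10% | 4.8% | 1.90 |
| 12% | 4.7% | 1.89 |
| 20% | 4.6% | 1.85 |
| 30% | 4.5% | 1.80 |
| 50% | 4.2% | 1.68 |
| 70% | 3.8% | 1.53 |
| 80% | 3.6% | 1.43 |

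A simulation with nested binomials at 1090 per arm (400,000 trials, Wald limit for non-inferiority, pooled one-sided z test for superiority) agrees: 4.8%, 4.4%, 4.1% and 3.6% at shares of 12%, 30%, 50% and 80%. Base rates of 13% and 15% give almost the same values. Two independent tests would give 1 − 0.975² = 4.94%, which nested endpoints cannot reach.

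**Non-inferiority on severity after a failed primary.** Take true PEP rates of 9.7% and 14.7%, exactly at the margin, so that the primary fails in about 97.5% of trials, with the same share in both arms and 1090 per arm.

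| Share | True severity difference (5 points × share) | P(primary fails and severity non-inferiority declared) |
|---|---|---|
| 12% | 0.6 points | 97.5% |
| 30% | 1.5 points | 96.4% |
| 50% | 2.5 points | 65.9% |
| 70% | 3.5 points | 21.9% |

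In every row the true severity difference is below 5 points, so the declaration is correct under the rule as written. If the severity margin is scaled to 5% × share, the probability falls to 1.8-2.4% (shares 20-50%, control rates 9.7-16.5%). If severity is truly 5 points worse, the unscaled rule declares non-inferiority after a primary failure in only 1.6-2.1% of trials. The large probabilities are thus a product of the margin. The missing order accounts for about 2 points.

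**The case against.** The plan does rank its endpoints. SAP 3.2 says that the study is designed to test the primary hypothesis, and there is one secondary efficacy endpoint. SAP 2 says that superiority is not the main interest. Whether a single subordinate endpoint needs familywise control is partly a matter of convention, and neither document promises it. This lowers the weight of the point but does not remove it: the ranking in SAP 3.2 neither conditions the secondary claim nor makes it descriptive, while Protocol 13.3 gives it the full declaration rule.

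The superiority sentence in Protocol 13.3 could also be read as requiring primary non-inferiority before any superiority test. That barely helps, because with equal arms the primary nearly always passes: the chance of a false superiority claim would still be 4.8%, 4.4% and 4.1% at shares of 12%, 30% and 50%.

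Two stronger readings are tempting. A reader might take the high probabilities of declaring severity non-inferior after a failed primary as an error rate. They are not: the true difference in those scenarios lies inside the margin being tested. A reader might also say that false superiority claims nearly double. That fits only small shares. At 80% the ratio is 1.43, and the documents do not supply the share.

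The calculations use the intention-to-treat sample only. They model neither the per-protocol requirement, which makes non-inferiority harder to claim, nor the conditional superiority tests at the interim looks in SAP 9.2.

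**Conclusion.** The point stands as a gap in the claim rules. Protocol 13.3 with SAP 9.1 and 9.3 allows two formal claims on moderate-severe PEP that nothing ties to the primary result.

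Its measurable cost is a rise in the chance of at least one false superiority claim from 2.5% to about 3.6-4.8%, under equal arms, 1090 per arm and an assumed moderate-severe share of 10-80%. The other consequence is one of interpretation: a failed primary may sit beside a formal severity claim. The documents do not show that such a claim would be false, and its likelihood is chiefly a matter of the borrowed 5% margin, which needs its own justification.

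This should be corrected, but it does not threaten the primary analysis.

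**What to change.** State one fixed sequence in SAP 9.3 and Protocol 13.3, each step at one-sided 2.5%, with formal claims stopping at the first failure. For example:

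1. PEP non-inferiority
2. moderate-severe PEP non-inferiority
3. PEP superiority
4. moderate-severe PEP superiority

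Results after the stopping point are reported as estimates with 95% intervals, without a formal claim. Alternatively, label the whole moderate-severe analysis as descriptive (estimate and 95% interval).

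A single sequence is preferable to pairing like with like (severity non-inferiority after PEP non-inferiority, severity superiority after PEP superiority). Pairing leaves PEP superiority and severity non-inferiority open in parallel once the primary passes. In an extreme case, with PEP equal and severity 5 points worse, the chance of any false claim is then still up to about 4.6%. Requiring only primary non-inferiority before severity superiority does not restore 2.5% either, as shown above.

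The cost is a short paragraph in each document. Sample size and the power of the primary non-inferiority test do not change. The downside is small: there is no formal severity claim if the primary fails, and each later claim depends on the steps before it. If a tighter severity margin is adopted, step 2 becomes harder to pass, so the order of steps 2 and 3 should be settled together with that margin.

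### SAP 9.3 lists stent characteristics and pancreatic stent placement as baseline variables: the characteristics have no estimable treatment interaction, and placement, if it means the prophylactic stent, nearly duplicates the randomised arm (secondary analyses only)

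*SAP*

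**What the plan says.** SAP 9.3 gives one list of baseline variables for the prognostic and subgroup analyses. Between biliary sphincterotomy and type of sphincter of Oddi dysfunction it contains "pancreatic stent placement, double wire technique, make/model/length/caliber of pancreatic stent, trainee involvement, prophylactic stent characteristics".

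The same procedure applies to every item:
- "Each covariate will be assessed individually first with a model that includes interaction effect with the treatment".
- "We also will be examining the parameter estimate of the treatment in the presence of the covariate". No selection step comes before this.
- A multivariable model follows, for which "a combination of statistical and clinical significance will be used for model inclusion", with goodness of fit deciding the final form. Its adjusted risk difference is compared with 5%. If the upper limit is 5% or more, "then non-inferiority of the treatments cannot be concluded in the presence of the particular covariates".
- All of this is done twice, once in the ITT sample and once in the per-protocol sample.

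Protocol 8.2.6 makes the prophylactic stent the component that differs between the arms. It leaves stent type to the endoscopist and collects stent details for exploratory work on PEP risk. It also describes stents placed to help biliary access or pancreatic sphincterotomy, which are taken out before the case ends if the subject is allocated to indomethacin alone.

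The primary analysis in SAP 9.1 is separate. Of the risk difference it says "This difference will not be adjusted for covariates", and "Non-inferiority can be claimed if both analysis populations show non-inferiority".

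**The concern.** A baseline covariate has to be fixed before assignment, or at least be unaffected by it. A prophylactic stent and its make, calibre and length arise after assignment and almost only in one arm. A model with treatment arm and such a variable either cannot be fitted or asks a different question: what arm does once the stent is held fixed. The trial asks what happens when the stent is omitted.

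At stake are the covariate-adjusted treatment estimates and the adjusted check against 5%. SAP 9.3 says that the assessment of prognostic variables is taken into account when the final results are interpreted. An estimate from which the stent effect has been removed could look reassuring beside a failed primary analysis. One with a greatly inflated standard error could cast doubt on a sound result.

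**Working it through.** **Inputs from the documents.** 1090 per arm (Protocol 1.0); combination PEP 9.7% (SAP 4.2); margin 5 points, judged by the upper limit of a two-sided 95% interval (SAP 4.1); non-compliance at most 5% (SAP 5.2). Protocol 3.1 says that failed placement raises PEP risk but gives no rate.

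**Assumptions.** f = share of failed placements, 2-5%; c = share stented in the indomethacin arm, 0-5% (2% in the base case); PEP after failed placement 9.7% to 30%.

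**Check of design inputs.** The SAP gives no figure for the 9.3 models, but its power statement in SAP 4.3 can be reproduced. Power = Φ(0.05/SE − 1.96), SE = √(2p(1−p)/650).
- p = 9.7%: SE 0.0164, power 86.1% (stated about 85%).
- p = 13%: SE 0.0187, power 76.4% (stated 76%).

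**Stent characteristics.** With f = 5% and c = 2%, unstented subjects number 0.05·1090 + 0.98·1090 = 1123 of 2180 (52%). None has a make, calibre or length. Among stented subjects, arm compares 0.02·1090 ≈ 22 with 0.95·1090 ≈ 1036. With c = 0 there is no such comparison and the interaction is not estimable. Coding unstented subjects as a category of their own only brings stent placement back in.

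**Stent placement, if prophylactic.** Correlation with arm: |r| = (1−f−c)/(2√(m(1−m))), m = (1−f+c)/2.
- Over the ranges above, |r| = 0.90 to 0.98 and VIF = 1/(1−r²) is about 5 to 26.
- f = 5%, c = 2%: |r| = 0.93, VIF 7.4.
- f = 5%, c = 0: the interaction model has rank 3 of 4 and cannot be estimated.
- In the per-protocol sample, if failed placement counts as crossover (SAP 5.4 does not say), stent placement equals arm and the two cannot both be fitted.

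**What the treatment parameter becomes.** Take a true +5 points caused entirely by the stent. Let s and u be PEP with and without a stent: 0.95s + 0.05u = 0.097 and 0.02s + 0.98u = 0.147, so s = 9.4% and u = 14.8%.
- Unadjusted OR = (0.147/0.853)/(0.097/0.903) = 1.60, log-odds SE 0.133, 95% CI 1.24-2.08.
- With stent placement in the model: OR about 1.0, SE 0.346, a ratio of 2.6. Over the f and c ranges the ratio is about 2.2 to 4.7.
- With the interaction, unstented as reference: 1068 subjects against about 54 failed placements. SE = √(1/(1068·0.148·0.852) + 1/(54.5·0.148·0.852)) = 0.39; 95% CI about 0.46-2.15 around an OR of 1.0. With stented as reference, 22 against 1036: SE 0.74, CI 0.23-4.27.

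**Adjusted check against 5%, true +5 points, f = 5%, c = 2%.** Simulated trials used a logistic model with arm and stent placement, a standardised risk difference and a delta-method interval. The stent term was kept at Wald p<0.05 (an assumption); otherwise the unadjusted interval was used. The check fails to warn when its upper limit is below 5%.

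| Assumed PEP after failed placement | Check fails to warn |
|---|---|
| 9.7% | about 4% |
| 14.8% (base case) | about 26% |
| 20% | 47-60% |
| 30% | about 90-95% |
| Unadjusted, for comparison | about 2-3% |

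The 9.7% row gives crossovers the indomethacin-arm rate and the 14.8% row the stented rate; the ranges for 20% and 30% cover both. The term is selected in 32% of base-case trials.

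**No true difference, all rates 9.7%.** Unadjusted SE = √(2·0.097·0.903/1090) = 0.0127. With the stent term always included, SE ≈ 0.0127·√7.4 = 0.035, and the chance that the upper limit falls below 5% is Φ(0.05/0.035 − 1.96), about 30%. In simulation the primary claim is met and the adjusted check vetoes it in about two-thirds of trials. With p<0.05 selection the false veto falls to 2.2%.

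**The case against.** The strongest reply is that no decision turns on this. The primary claim is unadjusted and needs both the ITT and the per-protocol sample. The adjusted model can only withhold support, and the SAP 9.3 risk score contains no stent item. That stands and keeps the point minor. A reader might infer that an adjusted pass could rescue a failed primary analysis; no passage allows it.

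Second, pancreatic stent placement may not mean the prophylactic stent. In the list it stands next to biliary sphincterotomy and double wire technique, and prophylactic stent characteristics are named separately. Protocol 8.2.6 describes access stents, so that reading is plausible. Under it, the collinearity and simulation figures fall away. The objection to the characteristics items remains.

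Third, the odds ratio near 1.0 is true by construction, because that scenario makes PEP depend only on stent status. It shows what the parameter measures, not how large the harm is. The simulated percentages rest on failed-placement rates and a selection rule that the documents do not give; the clinical-significance and goodness-of-fit steps were not modelled. It is tempting to conclude that the adjusted estimate is biased towards indomethacin alone by a known amount. The results do not support that: the harm runs from almost no false reassurance to nearly certain false reassurance, or to frequent false vetoes.

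Fourth, Protocol 8.2.6 already describes the work on stent characteristics as exploratory. That is right about purpose, but SAP 9.3 still puts them through the treatment models.

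**Conclusion.** The defect holds as a minor one, confined to secondary analyses. For the stent-characteristics items it is firm: they are post-assignment, absent in about half the sample, and their treatment interaction is not estimable apart from a few crossovers. For pancreatic stent placement it is conditional on the prophylactic reading. There, the treatment standard error is about 2.2 to 4.7 times larger with 2-5% failed placements and 0-5% crossovers, and the parameter no longer measures the effect of omitting the stent.

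Neither the size nor the direction of the harm can be fixed from the documents. At a true +5-point excess, failure to warn runs from about 4% to over 90% as the assumed PEP after failed placement rises from 9.7% to 30%. With no true difference, false vetoes run from about 2% to about two-thirds depending on how the term is selected. The primary non-inferiority claim is not affected.

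**What to change.** In SAP 9.3, delete pancreatic stent placement, stent make/model/length/calibre and prophylactic stent characteristics from the baseline-variable list, and therefore from the interaction models and the adjusted risk-difference model. Add a sentence such as: Prophylactic stent characteristics will be examined in relation to PEP among stented subjects only, as an exploratory analysis. This keeps the purpose stated in Protocol 8.2.6. If stents placed for access before randomisation were intended, name and define them as a separate variable.

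The cost is SAP wording. A separate access-stent variable may need a CRF field that distinguishes it from the prophylactic stent; the documents do not show whether one exists.

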## 4. NON-INFERIORITY MARGIN AND SAMPLE SIZE DETERMINATION FOR THE PRIMARY OBJECTIVE

### 4.1 Non-inferiority Margin

The non-inferiority margin is set at an absolute margin of 0.05; i.e., indomethacin alone will be considered non-inferior to the combination if it is shown that the upper limit of the two-sided 95% confidence interval of the absolute difference between the two PEP proportions (indomethacin – combination) is less than 5%. The value of this margin is based on a combination of statistical and clinical judgment and was chosen to ensure that the overall PEP proportion of the new treatment (indomethacin alone) demonstrates a clinically unimportant difference from the active comparator arm (the combination of stent and indomethacin) as well as a clinically relevant superiority over a putative placebo (i.e., stent alone). From a statistical perspective, the margin should retain at least 50% of the superiority of the combination of stent and indomethacin (the active control in the trial) when compared to stent alone. Our recent indomethacin RCT revealed that the risk-adjusted proportion of subjects with post-ERCP pancreatitis

in the combination of indomethacin and stent arm was 9.5% and that of stent alone was 15.7%. Unadjusted rates were 9.7% and 16.1%, respectively. Based on these results, the reduction of the combination arm on PEP as compared to stent alone is 6.4%. Therefore, taking a fraction of this value gives a non-inferiority margin ( $\delta$ ) of 3.2% ( $\delta = .5 \times 6.4$ ). This margin is a fraction of the effect of combination compared to stent alone as assessed in the previous trial.

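### SAP 9.3 attaches a non-inferiority verdict to a data-selected model whose candidate covariates include the stent itself, and no rule says which result prevails if it disagrees with SAP 9.1.

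*SAP*

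**What the plan says.** **The primary rule.** SAP 4.1: "The non-inferiority margin is set at an absolute margin of 0.05". SAP 9.1 analyses the observed risk difference (indomethacin alone minus combination): "This difference will not be adjusted for covariates". The test is made "at the one-sided 2.5% significance level by using the upper bound of the two-sided 95% confidence interval", and "Non-inferiority can be claimed if both analysis populations show non-inferiority", meaning ITT and per protocol. Covariate work is given a lower rank: "as a secondary analysis of the primary outcome, prognostic variables will be examined". Protocol 13.3 also bases the declaration on the observed risk difference and mentions no adjusted model.

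**The second verdict.** SAP 9.3 lists 20 candidate covariate entries, fits each with treatment in a logistic model for PEP, and looks at both the covariate and the treatment estimate. For the multivariable model, "a combination of statistical and clinical significance will be used for model inclusion". Then: "The final multivariable model will be based on goodness of fit criteria". No entry cut-off and no fit criterion is named. An adjusted risk difference with a 95% interval follows, in both samples, and "If the upper limit of this confidence interval is 5% or greater, then non-inferiority of the treatments cannot be concluded". The sentence ends by limiting this to the covariates in the model.

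**The link to the conclusion.** SAP 9.3 next describes a site-stratified interval with its own 5% rule. It says that this result, like the prognostic-variable assessment, will be weighed when the final results are interpreted. It does not say how, or which result prevails.

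**The candidates.** The list headed as baseline variables includes pancreatic stent placement, stent make, model, length and calibre, and prophylactic stent characteristics.

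**The concern.** Two analyses of the same endpoint use the same margin, and each carries a stated non-inferiority conclusion. The first is fixed in advance. The second depends on choices made after outcomes are known. If they disagree, the SAP leaves the trial team to decide what the trial showed, which a pre-specified margin is meant to prevent.

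The candidate list makes this more serious. Stent placement is what the arms differ by. A model holding both arm and stent placement no longer estimates the randomised contrast. It compares the arms at equal stent status, using only the few patients who did not receive their assigned strategy. Stent make or calibre is recorded only for patients who had a stent, so it is undefined for nearly all of the indomethacin-alone arm.

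In addition, Protocol 8.2.4 places randomisation during the ERCP, so some listed procedural variables may arise after assignment.

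**Working it through.** **1. The plan's own figures.** Equal rates p, n per arm: SE = √(2p(1−p)/n), power = Φ(0.05/SE − 1.96).
- n = 650, p = 9.7%: SE = 0.01642, power 86.1% (SAP 4.2: 85%).
- n = 650, p = 13%: SE = 0.01865, power 76.4% (SAP 4.3: 76%).
- n = 1090, 12.0% v 9.7%: 2.3% ± 1.96 × 1.331% = −0.3% to 4.9%, as in SAP 4.1.

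At n = 1090 the SAP 9.1 rule, applied to one sample, has power 97.6% at 9.7% and 93.5% at 13%. Nothing in SAP 9.3 enters this calculation.

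**2. Stent placement in the model: arithmetic.** Assume a stent in 95% of the combination arm (SAP 5.2 expects non-compliance of no more than 5%) and in 2% of the indomethacin-alone arm (assumption).
- Overall stent proportion: (0.95 + 0.02)/2 = 0.485.
- Covariance of arm and stent: 0.5 × 0.02 − 0.5 × 0.485 = −0.2325.
- r² = 0.2325² / (0.25 × 0.485 × 0.515) = 0.866.
- Variance inflation: 1/(1 − 0.866) ≈ 7.4.
- At 9.7% and 1090 per arm, SE rises from 0.01268 to 0.01268 × √7.44 = 0.0346, and the half-width to 6.8 points.
- To pass, the adjusted estimate must be below 5 − 6.8 = −1.8 points. With truly equal arms, Φ(−0.0178/0.0346) ≈ 0.30, so about 70% fail.
- Range at 9.7%: crossover of 5% in both arms gives inflation 5.3 and about 60% failing; 2% in both gives 12.8 and about 80%.

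**3. Stent placement in the model: simulation.** 1090 per arm, equal arms, 600 trials per setting, 5% and 2% crossover, no stent effect beyond arm, 15 binary covariates (9 prognostic) entered at p < 0.10.
- 9.7% rate: SAP 9.1 passed and the stent model failed in 63.5% of all trials. The unadjusted rule passed in 96.3%, so this is 63.5/96.3 = 66% of passing trials.
- 15% rate: 66.8% of all trials, or 66.8/89.7 = 74% of passing trials.

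A second simulation, with the same crossover figures, gave 65–84% of passing trials.

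**4. Pre-randomisation covariates only.** In the step 3 simulation without stent placement, the adjusted model contradicted a pass in 0.3% of trials (9.7% rate) and 1.0% (15% rate).

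To separate selection from adjustment, a further simulation used 15 candidates (10 prognostic, odds ratios 1.2–2.5, prevalences 10–50%), 1000 trials per setting and a true excess of 2 points. Share of trials passing the unadjusted ITT rule that then failed:

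| PEP rate | Fixed list of the 10 prognostic covariates | Screened at p < 0.10 | Any of four selection rules | Any of four minus fixed |
|---|---|---|---|---|
| 9.7% | 4.4% | 4.6% | 6.0% | 1.6 |
| 13% | 5.5% | 5.5% | 7.9% | 2.4 |
| 16.5% | 8.5% | 8.3% | 12.2% | 3.7 |

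The four rules were entry at p < 0.10, 0.05 or 0.01, or the best three covariates. Monte Carlo error is about 1 point. At 9.7% with equal arms, the fixed and screened models each failed in 0.6%. The documents give no 16.5% rate; it is an assumption.

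**5. Direction.** At a true difference of 5 points (9.7% v 14.7%, 1090 per arm, 600 trials), non-inferiority was claimed in 2.7% by the unadjusted rule and in 1.7% when the pre-randomisation adjusted model also had to pass.

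**The case against.** A reader might infer that SAP 9.3 lets a post hoc model withdraw or overturn the primary result. The documents do not say so. The sentence confines its verdict to the covariates in the model, SAP 9.1 ranks this work as secondary, and Protocol 13.3 relies on the observed difference alone. The stated goal of SAP 9.3 is to see how prognostic variables affect the primary analysis, which is a robustness check. Weighing a result in interpretation is not a veto. All of this stands. What remains is that no passage says that SAP 9.1 prevails.

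The candidates are named in advance, and if several qualify SAP 9.3 turns to a risk score with fixed weights. That also stands, so only the final choice is data-driven. But the score is itself only examined for inclusion, and a propensity score is added, so the model is still not fixed.

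A reader might also take the 6–12% in the any-of-four column as the effect of choosing covariates after seeing the data. It is not: a fixed list gives 4.4–8.5%, because crude and adjusted limits near a margin disagree anyway. Nor is the false-claim rate raised, since an added condition can only remove claims.

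Finally, the listed stent placement could be read as a temporary stent placed for access before randomisation. The SAP does not say this; its synopsis uses the term for the prophylactic intervention, and the list also names prophylactic stent characteristics.

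**Conclusion.** The point holds as a gap in precedence and specification. SAP 9.1 is a clear primary rule, but SAP 9.3 places beside it a second verdict from a model selected on outcomes by unnamed criteria and carries it into interpretation without a rule for disagreement.

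The larger part of the problem is the candidate list. Nothing in SAP 9.3 keeps stent placement out of the model, and with it about 64–84% of simulated truly non-inferior results fail the 5% test (the lower figure is a share of all trials, the upper of those passing). This rests on assumed crossover of 2–5% and moves with it.

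Without stent variables the effect is small: about 1% of passing trials with equal arms and 4–8% at a 2-point excess. Freedom to choose among four models adds about 2–4 points to what a fixed list gives. These figures depend on the assumed covariate prevalences and odds ratios. The risk is to power and clarity, not to type I error.

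**What to change.** - State in SAP 9.1 and 9.3 that the SAP 9.1 rule alone decides non-inferiority, and that the adjusted and site-stratified analyses are supportive.
- Remove the pass/fail sentence from SAP 9.3.
- Replace the selection procedure with one list of pre-randomisation covariates, fixed before unblinding, without stent placement, stent characteristics or any procedural variable that can arise after randomisation.
- Name one estimator: the standardised risk difference with its 95% interval, in ITT and per protocol.
- Label any model selected from the data as exploratory under SAP 9.4.

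The cost is SAP wording. Sample size, alpha and the power of the SAP 9.1 rule do not change. The data-driven model loses its formal verdict; the prognostic analysis itself can still be reported.
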